4.0 TREATMENT PLAN

4.1 Overview

[figure not shown]
Nivolumab and ipilimumab combination will be administered intravenously until disease progression or intolerable toxicity. Nivolumab will be given at 240mg over 30 minutes (-5 / +15 minutes) every 2 weeks starting with Cycle 1 Day 1 for the first 16 weeks (1 cycle = 12 weeks). Starting with Cycle 2 Day 29, nivolumab will be given at 480mg IV over 60 minutes (-10 / +15 minutes) every 4 weeks. Ipilimumab will be given at 1mg/Kg every 6 weeks starting with Cycle 1 Day 1 over approximately 90 minutes (-5 / +15 minutes). On days when both nivolumab and ipilimumab are administered, nivolumab should be given first, followed by ipilimumab about 30 minutes after completion of nivolumab. Patients will be assessed for response every 12 weeks (± 7 days). Note: Please refer to section 4.4 for patients who may continue treatment after initial progression.

4.2 Treatment Administration

Table 1 - Treatment Administration Summary

Agent	Pre-meds	Dose	Route	Schedule**	Cycle Length	Supportive Therapies
Nivolumab	None	240mg	IV infusion over ~30 minutes (-5 / +15 minutes, before ipilimumab)	C1: q2weeks C2D1 & C2D15	12 weeks (84 days)	As needed
Nivolumab	None	480mg	IV infusion over 60minutes (-10 / +15 minutes, before ipilimumab)	C2D29 & C2D57 C3+: D1, 29, 57		
Ipilimumab	None	1mg/Kg	IV infusion over ~90 minutes (-5 / +15 minutes) (30 min after completion of nivolumab)	Day1 & 43 of each cycle		

**See Table 2 for a simplified summary of the treatment schedule

4.2.1 Nivolumab

Treatment will be administered on an outpatient basis. Reported adverse events and potential risks are described below. No investigational or commercial agents or therapies other than those described below may be administered with the intent to treat the patient's malignancy.

For the first 8 doses (Cycle 1 + C2D1 + C2D15) nivolumab will be administered at a dose 240mg as an intravenous infusion over 30 minutes (-5 / + 15 minutes)

NU Study Number: NU 16N03
BMS Study Number: CA 209-802

every 14 days. Starting with C2D29, nivolumab will be administered at 480mg IV over 60 minutes (-10 / +15 minutes) every 28 days until disease progression, unacceptable toxicity, or withdrawal of consent.

There will be no dose escalations or reductions of nivolumab allowed. Patients may be dosed no less than 12 days or 24 days from the previous dose (for 240mg and 480mg doses respectively). There are no pre-medications recommended for nivolumab on the first cycle. If an acute infusion reaction is noted, subjects should be managed according to Section 4.3.3.

Nivolumab is to be administered as a 30-minute (-5 / +15 minutes) or 60-minute (-10 / +15 minutes) IV infusion (for 240mg and 480mg doses respectively), using a volumetric pump with a 0.2- 1.2 micron low-protein binding in-line filter at the protocol-specified dose. The drug can be diluted with 0.9% Sodium Chloride or 5% Dextrose for delivery but the total drug concentration of the solution cannot be below 0.35 mg/mL. It is not to be administered as an IV push or bolus injection. At the end of the infusion, flush the line with a sufficient quantity of normal saline.

Subjects will be monitored continuously for AEs while on study. Treatment delay or discontinuation will be based on specific laboratory and adverse event criteria.

4.2.2 Ipilimumab

Ipilimumab will be administered at a dose of 1mg/Kg as an intravenous infusion over approximately 90 minutes every 6 weeks until disease progression or unacceptable toxicity. Dosing will be based on weight at baseline, however if there is a weight change $\geq 10\%$, the dose should be adjusted accordingly. It should be administered approximately 30 minutes after nivolumab infusion.

There will be no dose escalations or reductions of ipilimumab allowed. There are no pre-medications recommended for ipilimumab on the first cycle. If an acute infusion reaction is noted subjects should be managed according to Section 4.3.3.

Ipilimumab is to be administered as a 90-minute IV infusion (a window of -5 / +15 minutes is allowed), using a volumetric pump with a 0.2/1.2 micron in-line filter at the protocol-specified dose. The drug can be diluted with 0.9% normal saline for delivery but the total drug concentration of the solution must be 1-2 mg/mL. It is not to be administered as an IV push or bolus injection. At the end of the infusion, flush the line with a sufficient quantity of normal saline.

Subjects will be monitored continuously for AEs while on study. Treatment delays or discontinuation will be based on specific laboratory and adverse event criteria.

4.3 Toxicity Management & Dose Delays/Modifications

Any patient who receives at least one dose of study therapy will be evaluable for toxicity endpoints. Each patient will be assessed for the development of toxicity according to the timeframe referenced in the Schedule of Events table). Toxicity will be assessed according to the NCI CTCAE v. 4.03.

4.3.1 Dose delays: Ipilimumab and/or nivolumab

Ipilimumab and/or nivolumab administration should be delayed for the following until resolution to \leq Grade 1 or baseline:

- Any Grade 2 non-skin, drug-related adverse event, except for fatigue and laboratory abnormalities
- Any Grade \geq 3 skin drug-related AE
- Any Grade \geq 3 drug-related laboratory abnormality with the following exceptions for lymphopenia, AST, ALT, or total bilirubin or asymptomatic amylase or lipase:
 - Grade 3 lymphopenia does not require a dose delay
 - If a participant has a baseline AST, ALT, or total bilirubin that is within normal limits, delay dosing for drug-related Grade 2 toxicity
 - If a participant has baseline AST, ALT, or total bilirubin within the Grade 1 toxicity range, delay dosing for drug-related Grade \geq 3 toxicity
 - Any Grade \geq 3 drug-related amylase or lipase abnormality that is not associated with symptoms or clinical manifestations of pancreatitis does not require dose delay.
- Any AE, laboratory abnormality or inter-current illness which, in the judgment of the investigator, warrants delaying the dose of study medication.

Participants that have drug-related toxicities that meet the criteria for dose delay, should have both drugs (ipilimumab and nivolumab) delayed until retreatment criteria are met. (Exceptions apply to the retreatment criteria after dose delay of ipilimumab and nivolumab for Grade \geq 3 amylase and lipase abnormalities that are not associated with symptoms or clinical manifestations of pancreatitis and that are attributed to ipilimumab alone.)

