4.3.2 Treatment discontinuation: Ipilimumab and/or nivolumab

Should the treating physician decide to discontinue treatment given suspicion for a drug-related side effect, the side effect should be attributed to one study drug to the best of the physician's ability. Either ipilimumab or nivolumab should be discontinued based on this attribution, or both if a definite attribution is not possible.

Ipilimumab and/or nivolumab should be discontinued permanently for the following:

- Any Grade 2 drug-related uveitis, eye pain, or blurred vision that does not respond to topical therapy and does not improve to Grade 1 severity within the re-treatment period OR requires systemic treatment
- Any Grade 3 non-skin, drug-related adverse event lasting > 7 days, with the following exceptions for laboratory abnormalities, drug-related uveitis, pneumonitis, bronchospasm, hypersensitivity reactions, infusion reactions, and endocrinopathies:
 - Grade 3 drug-related uveitis, pneumonitis, bronchospasm, hypersensitivity reaction, or infusion reaction **of any duration** (can be < 7 days) requires discontinuation
 - Grade 3 drug endocrinopathies adequately controlled with only physiologic hormone replacement do not require discontinuation
 - Grade 3 drug-related laboratory abnormalities do not require treatment discontinuation except:
 - Grade 3 drug-related thrombocytopenia > 7 days or associated with bleeding (aside from minor bleeds \leq Grade 1) requires discontinuation

NU Study Number: NU 16N03
BMS Study Number: CA 209-802

- Any drug-related liver function test (LFT) abnormality that meets the following criteria require discontinuation:
 - AST or ALT > 5-10 x ULN for > 2 weeks
 - AST or ALT > 10 xUL
 - Total bilirubin > 5 x ULN
 - Concurrent AST or ALT > 3 xULN and total bilirubin > 2 x ULN
- Any Grade 4 drug-related adverse event or laboratory abnormality, except for the following events which do not require discontinuation:
 - Grade 4 neutropenia < 7 days
 - Grade 4 lymphopenia or leukopenia
 - Isolated Grade 4 amylase or lipase abnormalities that are not associated with symptoms or clinical manifestations of pancreatitis. PI and Data Safety and Monitoring Committee (DSMC) should be consulted for Grade 4 amylase or lipase abnormalities.
 - Isolated Grade 4 electrolyte imbalances/abnormalities that are not associated with clinical sequelae and are corrected with supplementation/appropriate management within 72 hours of their onset

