 - Grade 4 drug related endocrinopathy adverse events, such as adrenal insufficiency, ACTH deficiency, hyper- or hypothyroidism, or glucose intolerance, which resolve or are adequately controlled with physiologic hormone replacement (corticosteroids, thyroid hormones) or glucose-controlling agents, respectively, may not require discontinuation.
- Any event that leads to interruption in dosing lasting > 6 weeks (42 days) from the previously required dose requires discontinuation, with the following exceptions:
 - Dosing interruptions to allow for prolonged steroid tapers to manage drug-related adverse events are allowed. Prior to re-initiating treatment in a subject with a dosing interruptions lasting > 6 weeks from the previous dose, the PI and DSMC must be consulted. Tumor assessments should continue as per protocol even if dosing is interrupted. Periodic study visits to assess safety and laboratory studies should also continue every 4 weeks or more frequently if clinically indicated during such dosing interruptions.
 - Dosing interruptions lasting > 6 weeks from the previous dose that occur for non-drug- related reasons may be allowed if approved by the PI and DSMC. Prior to re-initiating treatment in a subject with a dosing interruption lasting > 6 weeks, the PI and DSMC must be consulted. Tumor assessments should continue as per protocol even if dosing is interrupted. Periodic study visits to assess safety and laboratory studies should also continue every 4 weeks or more frequently if clinically indicated during such dosing interrupted.
 - Any adverse event, laboratory abnormality, or intercurrent illness, which in the judgment of the Investigator, presents a substantial clinical risk to the subject with continued nivolumab dosing.
 - If the patient is still receiving clinical benefit, he or she can hold drug for a maximum of 42 days (6 weeks), or 60 days with approval from the DSMC, and subsequently continue therapy following the original treatment schedule.

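### Dose rules: a persisting Grade 2 endocrinopathy controlled on hormone replacement can meet a stricter rule (hold, then stop) than a controlled Grade 3 or 4 one, so Sections 4.3.1, 4.3.2 and 4.7 need reconciling

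*Combined protocol and SAP*

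**What the plan says.** **Delay (Section 4.3.1).** Dosing "administration should be delayed for the following until resolution to" Grade 1 or lower, or baseline. The first listed trigger is "Any Grade 2 non-skin, drug-related adverse event, except for fatigue and laboratory abnormalities". Patients who meet a delay criterion for a drug-related toxicity "should have both drugs (ipilimumab and nivolumab) delayed until retreatment criteria are met". The one stated exception to those criteria ("Exceptions apply to the retreatment criteria after dose delay of ipilimumab and nivolumab for Grade" 3 or higher amylase and lipase changes without symptoms, attributed to ipilimumab alone) does not concern endocrinopathies.

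**Length of hold (Sections 4.3.2 and 4.7).** "Any event that leads to interruption in dosing lasting > 6 weeks (42 days) from the previously required dose requires discontinuation". Section 4.3.2 then lists ways round this limit:
- "Dosing interruptions to allow for prolonged steroid tapers to manage drug-related adverse events are allowed", with the PI and DSMC consulted before restart.
- Interruptions for reasons unrelated to the drug may be approved by the PI and DSMC.
- For a patient still benefiting, "he or she can hold drug for a maximum of 42 days (6 weeks), or 60 days with approval from the DSMC".

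Section 4.7 repeats the 42- and 60-day limits for toxicity holds, but writes the limit as six weeks or more, where Section 4.3.2 has more than six weeks.

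**Stop by grade (Section 4.3.2).** "Grade 3 drug endocrinopathies adequately controlled with only physiologic hormone replacement do not require discontinuation". For Grade 4 endocrinopathies that resolve or are adequately controlled, the wording is permissive: they may not need a stop. When a stop is made for a suspected drug effect, it applies to the drug held responsible, and to both only if attribution is not possible.

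**Stage 1 (Section 10.2).** ACC accrual ends if 7 or more of the first 15 patients are withdrawn before 24 weeks of treatment for any reason except withdrawn consent. Toxicity and intolerance are named among the reasons.

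**The concern.** The stop rule recognises that an endocrinopathy can be controlled by replacement without resolving, and makes an exception for it at Grades 3 and 4. The delay rule has no matching exception at Grade 2, and its exit condition is a fall in grade or a return to baseline. A patient whose event is controlled but still graded 2 has no written way back to dosing, and the hold then runs into the interruption limit.

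Two things are at stake. A patient may lose one or both drugs for an event milder than one the protocol allows to continue. And the stage-1 decision counts early withdrawals of any cause, so a withdrawal produced by the rule wording counts the same as one caused by progression. Sites that resolve the wording differently would also make that count less comparable across patients.

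**Working it through.** **1. The rules side by side, for an endocrinopathy controlled on replacement**

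| Grade | Section 4.3.1: hold? | Section 4.3.2: stop by grade? | 42/60-day limit (4.3.2, 4.7) |
|---|---|---|---|
| 2, persisting | Yes, both drugs, until Grade 1 or baseline | No grade-based rule for it | Reached if the grade does not fall |
| 3 | Not a listed trigger for non-skin, non-laboratory events; investigator judgment only | Expressly spared | Reached only if dosing is held on judgment |
| 4 | As Grade 3 | May be spared | As Grade 3 |

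The Grade 3 and 4 exceptions belong to the grade-based stop items, not to the interruption-length item. The two sets of rules do not negate each other sentence by sentence. The defect is a missing exception that inverts the order of strictness.

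**2. Can a controlled event keep its grade?** The documents do not reproduce the CTCAE grading, so this is an assumption. Section 4.3.2 points that way. Its Grade 3 item concerns events lasting more than 7 days and still needs an exception for controlled ones, and its Grade 4 item lists resolving and being adequately controlled as alternatives. The protocol's own wording thus treats control as different from resolution.

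**3. Do the exceptions close the gap?** The steroid-taper exception helps only if a taper is under way. The non-drug exception does not apply to a drug-related event. The DSMC extension moves the limit from 6 × 7 = 42 days to 60 days; for an event that does not fall in grade, it postpones the stop. A return to baseline helps a patient enrolled with hypothyroidism already on replacement (allowed by Section 3.2.6), but not one who develops it on study.

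**4. Timing.** Twenty-four weeks is 24 × 7 = 168 days. For the stop to fall before then, the hold must begin by about day 168 − 42 = 126, or day 168 − 60 = 108 with the extension.

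**5. Effect on stage 1.** First, the plan's own figures. With stage-1 stopping at 7 or fewer successes in 15 and rejection at 24 or fewer in 43, exact binomial sums give:
- early termination at 0.45: 0.6535 (plan 0.654);
- expected size: 15 + (1 − 0.6535) × 28 = 24.70 (plan 24.70);
- type I error: 0.0481 (plan 0.048);
- power at 0.65: 0.8035 (plan 1 − 0.196 = 0.804).

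The rule as written closes at 7 or more withdrawals, which means 8 or fewer successes. That is one success stricter than the boundary behind the plan's figures. This is a separate matter, but it sets the starting value here.

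Let q be the share of otherwise successful patients taken off all treatment before week 24 by the hold-then-stop sequence. The success probability becomes 0.65 × (1 − q), and the closing probability is P(X ≤ 8) with X binomial(15, 0.65 × (1 − q)). The q values are illustrative.

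| q | Success probability | P(close), written rule (≤ 8) | P(close), boundary behind the plan's figures (≤ 7) |
|---|---|---|---|
| 0 | 0.650 | 0.245 | 0.113 |
| 0.01 | 0.6435 | 0.263 | 0.124 |
| 0.02 | 0.637 | 0.280 | 0.136 |
| 0.05 | 0.6175 | 0.337 | 0.174 |

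**The case against.** The best defence is that nothing in Section 4.3.2 promises continued treatment after a long Grade 2 hold. The interruption limit applies to any event, and the Grade 3 and 4 exceptions answer a different question. That is right as a reading of the structure, and it rules out calling this a direct contradiction. It does not explain why the milder event should have the harder path. Reading the delay trigger as Grade 2 or higher does not help either: a controlled Grade 3 event that kept its grade would then also be held into the 42-day limit, and its exception would have little effect.

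A reader might infer four stronger things that the documents do not support.
- **That a permanent stop of both drugs is forced at six weeks.** The taper exception, the 60-day extension and the one-drug stop by attribution all stand against this. A patient continuing on one drug is not clearly withdrawn in the sense of Section 10.2.
- **That retreatment criteria are missing altogether.** The opening condition of Section 4.3.1 can serve as the criterion, and the endocrinopathy chart in Appendix D is not visible in the text available. It may address resumption, so it cannot be used either way.
- **That the amylase and lipase statements in Section 4.3.1 conflict.** One says a delay is not required. The other can govern retreatment after a delay made on investigator judgment, which the last item of that list allows.
- **That the number of affected patients can be estimated.** Section 8.2.10 places hypothyroidism, hypopituitarism and adrenal insufficiency below 10% for ipilimumab alone. That is not the rate of persistent Grade 2 events on the combination that end all treatment before week 24.

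**Conclusion.** The concern holds as a gap between rules. Followed as written, Sections 4.3.1, 4.3.2 and 4.7 can take a patient with a controlled Grade 2 endocrinopathy off one or both drugs, while Section 4.3.2 expressly spares a controlled Grade 3 event and may spare a Grade 4 one. This rests on one assumption, that the controlled event remains Grade 2, which the protocol's wording makes plausible but does not establish.

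The effect on stage 1 is real in direction and unknown in size. It needs a stop of all treatment before week 24. Under the written rule, the illustrative losses of 1% to 5% of successes add about 0.02 to 0.09 to the chance of closing an effective regimen (0.263 − 0.245 = 0.018; 0.337 − 0.245 = 0.092). No figure in the documents says where in that range, or outside it, the trial would fall. The point merits correction because it changes what is done to patients and what is counted, and the remedy is cheap.

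**What to change.** Reconcile Sections 4.3.1, 4.3.2 and 4.7 and the endocrinopathy algorithm in Appendix D, so that one consistent delay, resume and stop action follows at each grade for an endocrinopathy controlled on hormone replacement. The clinical team decides what that action is.

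In the same edit:
- state in Section 4.3.1 whether the retreatment criteria are the Grade 1-or-baseline condition or something else;
- align the six-week limit, which is strictly more than six weeks in Section 4.3.2 and six weeks or more in Section 4.7.

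The cost is a protocol wording amendment with its usual approvals and notice to sites. It needs no new procedures, visits or data, and no change to the sample size.

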4.3.2 Treatment discontinuation: Ipilimumab and/or nivolumab

Should the treating physician decide to discontinue treatment given suspicion for a drug-related side effect, the side effect should be attributed to one study drug to the best of the physician's ability. Either ipilimumab or nivolumab should be discontinued based on this attribution, or both if a definite attribution is not possible.

Ipilimumab and/or nivolumab should be discontinued permanently for the following:

- Any Grade 2 drug-related uveitis, eye pain, or blurred vision that does not respond to topical therapy and does not improve to Grade 1 severity within the re-treatment period OR requires systemic treatment
- Any Grade 3 non-skin, drug-related adverse event lasting > 7 days, with the following exceptions for laboratory abnormalities, drug-related uveitis, pneumonitis, bronchospasm, hypersensitivity reactions, infusion reactions, and endocrinopathies:
 - Grade 3 drug-related uveitis, pneumonitis, bronchospasm, hypersensitivity reaction, or infusion reaction **of any duration** (can be < 7 days) requires discontinuation
 - Grade 3 drug endocrinopathies adequately controlled with only physiologic hormone replacement do not require discontinuation
 - Grade 3 drug-related laboratory abnormalities do not require treatment discontinuation except:
 - Grade 3 drug-related thrombocytopenia > 7 days or associated with bleeding (aside from minor bleeds \leq Grade 1) requires discontinuation

NU Study Number: NU 16N03
BMS Study Number: CA 209-802

- Any drug-related liver function test (LFT) abnormality that meets the following criteria require discontinuation:
 - AST or ALT > 5-10 x ULN for > 2 weeks
 - AST or ALT > 10 xUL
 - Total bilirubin > 5 x ULN
 - Concurrent AST or ALT > 3 xULN and total bilirubin > 2 x ULN
- Any Grade 4 drug-related adverse event or laboratory abnormality, except for the following events which do not require discontinuation:
 - Grade 4 neutropenia < 7 days
 - Grade 4 lymphopenia or leukopenia
 - Isolated Grade 4 amylase or lipase abnormalities that are not associated with symptoms or clinical manifestations of pancreatitis. PI and Data Safety and Monitoring Committee (DSMC) should be consulted for Grade 4 amylase or lipase abnormalities.
 - Isolated Grade 4 electrolyte imbalances/abnormalities that are not associated with clinical sequelae and are corrected with supplementation/appropriate management within 72 hours of their onset
 - Grade 4 drug related endocrinopathy adverse events, such as adrenal insufficiency, ACTH deficiency, hyper- or hypothyroidism, or glucose intolerance, which resolve or are adequately controlled with physiologic hormone replacement (corticosteroids, thyroid hormones) or glucose-controlling agents, respectively, may not require discontinuation.
- Any event that leads to interruption in dosing lasting > 6 weeks (42 days) from the previously required dose requires discontinuation, with the following exceptions:
 - Dosing interruptions to allow for prolonged steroid tapers to manage drug-related adverse events are allowed. Prior to re-initiating treatment in a subject with a dosing interruptions lasting > 6 weeks from the previous dose, the PI and DSMC must be consulted. Tumor assessments should continue as per protocol even if dosing is interrupted. Periodic study visits to assess safety and laboratory studies should also continue every 4 weeks or more frequently if clinically indicated during such dosing interruptions.
 - Dosing interruptions lasting > 6 weeks from the previous dose that occur for non-drug- related reasons may be allowed if approved by the PI and DSMC. Prior to re-initiating treatment in a subject with a dosing interruption lasting > 6 weeks, the PI and DSMC must be consulted. Tumor assessments should continue as per protocol even if dosing is interrupted. Periodic study visits to assess safety and laboratory studies should also continue every 4 weeks or more frequently if clinically indicated during such dosing interrupted.
 - Any adverse event, laboratory abnormality, or intercurrent illness, which in the judgment of the Investigator, presents a substantial clinical risk to the subject with continued nivolumab dosing.
 - If the patient is still receiving clinical benefit, he or she can hold drug for a maximum of 42 days (6 weeks), or 60 days with approval from the DSMC, and subsequently continue therapy following the original treatment schedule.

